10.7. Appendix 7: ECG Findings of Potential Clinical Concern

ECG Findings That May Qualify as AEs

Marked sinus bradycardia (rate <40 bpm) lasting minutes.New PR interval prolongation >280 msec.New prolongation of QTcF to >480 msec (absolute) or by \geq60 msec from baseline.New-onset atrial flutter or fibrillation, with controlled ventricular response rate: ie, rate <120 bpm.New-onset type I second-degree (Wenckebach) AV block of >30 seconds' duration.Frequent premature ventricular complexes (PVCs), triplets, or short intervals (<30 seconds) of consecutive ventricular complexes.
ECG Findings That May Qualify as SAEs

QTcF prolongation >500 msec.New ST-T changes suggestive of myocardial ischemia.New-onset left bundle branch block (QRS >120 msec).New-onset right bundle branch block (QRS >120 msec).Symptomatic bradycardia.Asystole:
In awake, symptom-free participants in sinus rhythm, with documented periods of asystole \geq3.0 seconds or any escape rate <40 bpm, or with an escape rhythm that is below the AV node.In awake, symptom-free participants with atrial fibrillation and bradycardia with 1 or more pauses of at least 5 seconds or longer.Atrial flutter or fibrillation, with rapid ventricular response rate: rapid = rate >120 bpm.Sustained supraventricular tachycardia (rate >120 bpm) ("sustained" = short duration with relevant symptoms or lasting >1 minute).Ventricular rhythms >30 seconds' duration, including idioventricular rhythm (rate <40 bpm), accelerated idioventricular rhythm (40 < x <100), and

monomorphic/polymorphic ventricular tachycardia >100 bpm (such as torsades de pointes).

- Type II second-degree (Mobitz II) AV block.
- Complete (third-degree) heart block.

ECG Findings That Qualify as SAEs

- Change in pattern suggestive of new myocardial infarction.
- Sustained ventricular tachyarrhythmias (>30 seconds' duration).
- Second- or third-degree AV block requiring pacemaker placement.
- Asystolic pauses requiring pacemaker placement.
- Atrial flutter or fibrillation with rapid ventricular response requiring cardioversion.
- Ventricular fibrillation/flutter.
- At the discretion of the investigator, any arrhythmia classified as an adverse experience.

The enumerated list of major events of potential clinical concern are recommended as “alerts” or notifications from the core ECG laboratory to the investigator and Pfizer study team, and not to be considered as all inclusive of what to be reported as AEs/SAEs.

10.8. Appendix 8: Prohibited Prior/Concomitant Medications

The following medications are prohibited until the follow-up visit (ie, 28-35 days after the last dose), unless stated otherwise. If a participant receives a prohibited medication, the investigator should contact the sponsor clinician or sponsor medical monitor to determine if the participant should be included in the study.

Drug Classes and/or Drugs	Timeframe of Restriction
GLP-1R agonists.	90 days prior to Screening Visit S1
DPP-4 inhibitors, pramlintide, repaglinide.	Screening Visit (S1) to Follow Up visit
Systemic glucocorticoids such as prednisone, dexamethasone, triamcinolone, budesonide, betamethasone. Note : As an exception, steroid-containing inhalers, nasal sprays and topical formulations are permitted.	Screening Visit (S1) to Follow Up visit
Immunosuppressants such as cyclosporine and tacrolimus.	Screening Visit (S1) to Follow Up visit
Rosuvastatin. Note : Other statins are permitted.	Day 1 (day of dosing)
Sulfasalazine (sensitive BCRP substrate)	Day 1 (day of dosing)
Use of chronic agents which are clinically significant OATP inhibitors (eg, cyclosporine, gemfibrozil, rifampin).	Screening Visit (S1) o Follow Up visit
Use of chronic agents which are potent inducers of CYP3A (eg, rifampin, phenytoin, carbamazepine, phenobarbital).	Screening Visit (S1) to Follow Up visit
Use of potent CYP3A4 inhibitors (eg, ritonavir, indinavir, itraconazole, clarithromycin).	Screening Visit (S1) to Follow Up visit
Use of moderate CYP3A4 inducers (eg, efavirenz, lopinavir, elagolix).	Screening Visit (S1) to Follow Up visit
Use of moderate CYP3A4 inhibitors (eg, diltiazem, verapamil, erythromycin, fluconazole).	Screening Visit (S1) to Follow Up visit

10.9. Appendix 9: Proposed Chronology of Procedures

For the procedures described below, where multiple procedures are scheduled at the same timepoint(s) relative to dosing, the following chronology of events should be adhered to:

- 12-lead ECG: obtain prior to vital signs assessment, blood samples, and prior to dosing (except for post-dose collection) (see [Section 8.2.3](#));
- Vital Signs (BP, PR, temperature): obtain after 12-lead ECG collection but prior to obtaining blood samples and prior to dosing (except for post-dose collection) (see [Section 8.2.2](#));
- Fasting blood samples [for safety (see [Section 8.2.7](#)), PK (see [Section 8.5](#)), exploratory biomarkers (see [Section 8.8](#)) and banked biospecimens (see [Section 8.7.1](#))]: after assessment of 12-lead ECG and vital signs but prior to dosing;
- For the random, post dose PK blood collection to occur approximately 2 to 6 hours post dose (see [Section 8.5](#)): if collection time coincides with time of a meal/snack, these blood samples should be collected just prior to the meal/snack;
- Other pre-dose procedures: obtain sample/perform procedure as close as possible to the scheduled time, but may be obtained before or after blood sample collection(s);
- Dosing: must occur with the morning meal; and where applicable, after any pre-dose blood sample collection(s).

10.10. Appendix 10: Abbreviations

The following is a list of abbreviations that may be used in the protocol.

	Term
Abs	absolute
AE	adverse event
Ae ₂₄	total amount of unchanged drug excreted in the urine over 24 hours
Ae ₂₄ %	total amount of unchanged drug excreted in the urine over 24 hours, expressed as percent of dose
ALT	alanine aminotransferase
AM	Morning
ANOVA	analysis of variance
AST	aspartate aminotransferase
AUC ₂₄	area under the plasma concentration-time profile from time 0 to time 24 hours
AUC _{inf}	area under the plasma concentration-time profile from time zero extrapolated to infinite time
AUC _{inf,u}	unbound area under the plasma concentration-time profile from time zero extrapolated to infinite time
AUC _{last}	area under the plasma concentration-time profile from time zero to the time of the last quantifiable concentration (C _{last}).
AUC _{last,u}	unbound area under the plasma concentration-time profile from time zero to the time of the last quantifiable concentration
AV	Atrioventricular
BBS	Biospecimen Banking System
BCRP	breast cancer resistance protein
β-hCG	beta-human chorionic gonadotropin
BID	twice daily
BMI	body mass index
BP	blood pressure
bpm	beats per minute
BSA	body surface area
BUN	blood urea nitrogen
cAMP	cyclic adenosine monophosphate
CFB	change from baseline
CFR	Code of Federal Regulations
CI	confidence interval
CIOMS	Council for International Organizations of Medical Sciences
CK	creatinine kinase
CKD	chronic kidney disease
CKD-EPI	Chronic Kidney Disease Epidemiology Collaboration equation
CL _u /F	apparent clearance of unbound drug after oral administration
CL _r	renal clearance

	Term
CL/F	apparent clearance
C _{max}	maximum observed concentration
C _{max,u}	maximum observed concentration of unbound drug
CO ₂	carbon dioxide (bicarbonate)
CONSORT	Consolidated Standards of Reporting Trials
COVID-19	coronavirus disease 2019
CP-I	coproporphyrin I
CRF	case report form
CRO	contract research organization
CRU	clinical research unit
CSR	Clinical Study Report
CT	clinical trial
%CV	percent coefficient of variation
CYP	cytochrome P450
DBP	diastolic blood pressure
DPP	Dipeptidyl Peptidase
DDI	drug-drug interactions
DILI	drug-induced liver injury
DMC	Data Monitoring Committee
DNA	deoxyribonucleic acid
EC	ethics committee
ECG	electrocardiogram
eCRF	electronic case report form
EDP	exposure during pregnancy
EFD	embryo fetal developmental
EMA	European Medicines Agency
eGFR	estimated glomerular filtration rate
ET	early termination
EU	European Union
EudraCT	European Clinical Trials Database
FDA	Food and Drug Administration
FSBG	fingerstick blood glucose
FPG	fasting plasma glucose
FSH	follicle-stimulating hormone
fu	fraction of unbound drug in plasma
FU	follow up
GCP	Good Clinical Practice
GGT	gamma-glutamyl transferase
GLP-1	glucagon-like peptide-1
GLP-1R	glucagon-like peptide-1 receptor
H or h or hr	hour
HAE	hypoglycemic adverse event

	Term
HbA1c	glycated hemoglobin
HIPAA	Health Insurance Portability and Accountability Act
HRT	hormone replacement therapy
IB	Investigator's Brochure
ICD	informed consent document
ICH	International Council for Harmonisation
IND	investigational new drug application
INR	international normalized ratio
IP	investigational product
IP manual	investigational product manual
IR	immediate release
IRB	Institutional Review Board
IUD	intrauterine device
IUS	intrauterine hormone-releasing system
IV	intravenous
IVGTT	intravenous glucose tolerance test
K ₂ EDTA	dipotassium ethylenediaminetetraacetic acid
LFT	liver function test
Log _e	natural logarithm
MATE	multidrug and toxin extrusion protein
MCH	mean corpuscular hemoglobin
MCHC	mean corpuscular hemoglobin concentration
MCV	mean corpuscular volume
MDRD	Modification of Diet in Renal Disease
MDR1	multidrug resistance mutation
MEN2	multiple endocrine neoplasia syndrome type 2
mg/kg	milligrams per kilogram
msec	millisecond
MTC	medullary thyroid carcinoma
N/A	not applicable
NOAEL	no-observed-adverse-effect level
OATP	organic anion transporting polypeptides
OCT2	organic cation transporter 2
PCD	primary completion date
PD	pharmacodynamic(s)
PE	physical examination
PGx	pharmacogenomic(s)
PK	pharmacokinetic(s)
PR	ECG parameter/interval
PT	prothrombin time
PVC	premature ventricular contraction/complex
QRS	ECG parameter/interval

	Term
QT	time from the beginning of the QRS complex to the end of the T wave
QTcF	QTc corrected using Fridericia's formula
qual	qualitative
R _{ac}	accumulation ratio
RBC	red blood cell
RNA	ribonucleic acid
S1	screening visit 1
S2	screening visit 2
SAE	serious adverse event
SAP	Statistical Analysis Plan
SARS-CoV-2	severe acute respiratory syndrome coronavirus 2
SBP	Systolic blood pressure
SCr	serum creatinine
SMP	study monitoring plan
SoA	schedule of activities
SOP	standard operating procedure
SRSD	single reference safety document
SSID	Single Subject Identifier
ST	slow titration
SToD	study team on demand
SUSAR	Suspected Unexpected Serious Adverse Reaction
t _{1/2}	terminal phase half-life
TBili	total bilirubin
TEAE	treatment-emergent adverse event
THC	tetrahydrocannabinol
T _{max}	time to maximum observed concentration
T2DM	type 2 diabetes mellitus
UGT	uridine 5'-diphospho-glucuronosyltransferase
ULN	upper limit of normal
US	United States
Vz/F	apparent volume of distribution
Vz, _u /F	Unbound Vz/F
WBC	white blood cell
WOCBP	woman of childbearing potential

1. VERSION HISTORY

Table 1. Summary of Changes

Version/ Date	Associated Protocol Amendment	Rationale	Specific Changes
1.0 10 Dec 2020	Original 13 Oct 2020	N/A	N/A

2. INTRODUCTION

This statistical analysis plan (SAP) provides the detailed methodology for summary and statistical analyses of the data collected in Study C3421012. This document may modify the plans outlined in the protocol; however, any major modifications of the primary endpoint definition or its analysis will also be reflected in a protocol amendment.

2.1. Study Objectives, Endpoints, and Estimands

Objectives	Endpoints
Primary:	Primary:

 To compare the PK of PF-06882961 following administration of a single oral dose in adult participants with T2DM and varying degrees of renal impairment relative to T2DM participants without renal impairment. 	
 Plasma: C_{max}, AUC_{inf}, AUC_{last}, fu, as data permit
Secondary:	Secondary:

 To compare additional PK parameters of PF-06882961 following administration of a single oral dose in adult participants with T2DM and varying degrees of renal impairment relative to T2DM participants without renal impairment. 	
 Plasma: $C_{max,u}$, $AUC_{inf,u}$, $AUC_{last,u}$, CL/F, CL_u/F, V_z/F, $V_{z,u}/F$, T_{max}, $t_{1/2}$, as data permit

 To evaluate the safety and tolerability of a single oral dose of PF-06882961 in T2DM participants with varying degrees of renal impairment and in participants with normal renal function. 	
 Incidence and severity of treatment-emergent AEs, clinical laboratory abnormalities, vital signs (blood pressure and pulse rate), ECG parameters (heart rate, QT, QTcF, PR and QRS intervals).

Tertiary/Exploratory:	Tertiary/Exploratory:

 To compare urine PK parameters of PF-06882961 following administration of a single oral dose in adult participants with T2DM and varying degrees of renal impairment relative to T2DM participants without renal impairment. 	
 Urine: CL_r, Ae_{24}, $Ae_{24\%}$

 To compare the PK of PF-06882961 following administration of a single oral dose in adult participants with T2DM and normal renal function relative to healthy participants with normal renal function. 	
 Plasma: C_{max}, T_{max}, AUC_{inf}, AUC_{last}, CL/F, V_z/F, $t_{1/2}$, fu, as data permit Urine: CL_r, Ae_{24}, $Ae_{24\%}$

 To explore the relationship of markers of innate OATP activity in adult participants with T2DM and varying degrees of renal impairment relative to participants with normal renal function. 	
 CP-I concentration

 To enable exploratory research through collection of banked biospecimens, unless prohibited by local regulations or ethics committee decision. 	
 Potential results from exploratory analysis of banked biospecimens (these results may or may not be generated in the context of the present study).

There are no estimands for this study.

2.2. Study Design

This Phase 1, open-label, single-dose, parallel group, multi-site study will assess the effect of varying degrees of renal impairment on the PK, safety and tolerability of PF-06882961 after a single oral dose of 20 mg administered in a fed state.

Approximately 40 participants will be enrolled in the study. Refer to [Table 2](#) below for details of study groups. Due to the potential difficulty in recruiting T2DM patients with estimated glomerular filtration rate (eGFR) <30 mL/min, the number of participants to be enrolled in this group is flexible (6 to 8 participants).

This study will permit enrollment of 2-4 participants on dialysis, as part of the severe renal impairment group, to assist in recruitment of patients with more advanced renal impairment and to permit assessment of the PK of PF-06882961 in participants with the highest degree of renal impairment. Since PF-06882961 has a large unbound non-renal clearance and a large unbound volume of distribution, dialysis is not expected to significantly impact the clearance of PF-06882961 and therefore the dialysis clearance of PF-06882961 will not be characterized in this study. Thus, Day 1, per the schedule of activities, will occur in dialysis patients on a day in which dialysis is not administered.

Table 2. Study Groups

Group	Disease State	Renal Impairment	No. of Participants	eGFR^a (mL/min)
1	None (healthy)	None (Normal Renal Function)	8	≥90
2	T2DM	None (Normal Renal Function)	8	≥90
3	T2DM	Mild	8	60-89
4	T2DM	Moderate	8	30-59
5	T2DM	Severe	6-8 ^b	<30

*a. Estimate of eGFR based on the SCr-based CKD-Epi equation. The eGFR will be multiplied by each participant's ratio of BSA/1.73 to obtain the BSA-unnormalized eGFR value. The average of the 2 unnormalized eGFR values from S1 and S2 will be used for study enrollment and group placement. **Note:** participants on dialysis will be placed in Group 5 regardless of unnormalized eGFR from S1 and S2.*

[figure not shown]
b. This includes approximately 4 participants not on dialysis and 2-4 participants on dialysis.

Screening will occur within 28 days of the first dose of study intervention on Day 1. All participants will provide informed consent and undergo Screening evaluations to determine their eligibility. All participants who are not on dialysis must have stable renal function to enter the study, defined as ≤25% difference between 2 measurements of BSA-unnormalized eGFR obtained from the 2 screening visits, S1 and S2 as listed in the schedule of activities. As indicated in Table 2, the estimate of eGFR will be based on the SCr-based CKD-Epi equation, defined in Section 3.2.1.

*Participants with T2DM and varying degrees of renal impairment (Groups 3-5) will be recruited and enrolled first. An average value for age and weight for these groups will be determined and participants in Groups 1-2 will be recruited to match the average demographics (at a minimum, age and weight, and as much as practically possible gender) across the pooled Groups 3-5. Recruitment for participants in Groups 1-2 may start when approximately 75% of total participants across Groups 3-5 (ie, approximately 17-18) have been dosed. Approval from the sponsor must be garnered **before** proceeding with dosing participants in Groups 1 and 2.*

Refer to Figure 1 for study schema.

Participants who discontinue from the study before completing all assessments may be replaced at the discretion of the investigator and sponsor.

Figure 1. Study Schema

*Screening period is \leq 28 days from dosing on Day 1.

3. ENDPOINTS AND BASELINE VARIABLES: DEFINITIONS AND CONVENTIONS

Blood samples for PK analysis of PF-06882961 will be collected according to the Schedule of Activities given in the protocol.

PK parameters will be calculated (if possible) from the concentration-time data using standard non-compartmental methods.

3.1. Primary Endpoint(s)

- PF-06882961 Plasma Pharmacokinetic parameters: C_{max} , AUC_{inf} , AUC_{last} , fu , as data permit.

The plasma PK parameters in Table 3 will be determined using standard non-compartmental methods:

Table 3. Summary of Plasma PK Parameters of PF-06882961 to be calculated

Parameter	Analysis Scale	PF-06882961 20mg
C_{max}	ln	A, D
AUC_{inf}^*	ln	A, D
AUC_{last}	ln	A, D
fu	ln	A, D

*=if data permits. Abbreviations: A = analyzed using a statistical model; D=displayed with descriptive statistics as outlined in [Table 7](#) in Section [6.1.1.1](#); ln=natural-log transformed; R=raw (untransformed).

3.2. Secondary Endpoint(s)

3.2.1. Additional Plasma PK parameters of PF-06882961

- $C_{max,u}$, $AUC_{inf,u}$, $AUC_{last,u}$, CL/F , CL_u/F , V_z/F , $V_{z,u}/F$, T_{max} , $t_{1/2}$, as data permit

The plasma PK parameters for PF-06882961 in Table 4 will be determined using standard non-compartmental methods:

Table 4. Summary of Additional Plasma PK parameters of PF-06882961 to be calculated

Parameter	Analysis Scale	PF-06882961 20mg
CL/F^*	ln	A, D
V_z/F^*	ln	D
T_{max}	R	D
$t_{1/2}^*$	R	D

*=if data permits. Abbreviations: A = analyzed using a statistical model; D=displayed with descriptive statistics as outlined in [Table 8](#) in Section [6.2.1](#); ln=natural-log transformed; R=raw (untransformed).

The plasma PK parameters for unbound PF-06882961 will be calculated as described in Table 5:

Table 5. Summary of Plasma PK parameters of Unbound PF-06882961 to be calculated

Parameter	Method of Determination	Analysis Scale	PF-06882961 20 mg
$AUC_{last,u}$	$fu \times AUC_{last}$	ln	D
$AUC_{inf,u}^*$	$fu \times AUC_{inf}$	ln	D
$C_{max,u}$	$fu \times C_{max}$	ln	D
CL_u/F^*	$Dose/(AUC_{inf,u})$	ln	A, D
$V_{z,u}/F^*$	$Dose/(AUC_{inf,u} \times k_{el})$	ln	D

*=if data permits. Abbreviations: A = analyzed using a statistical model, D=displayed with descriptive statistics as outlined in [Table 8](#) in Section [6.2.1](#); ln=natural-log transformed, R=raw (untransformed).

For the linear regression analysis assessing the relationship between CL/F , CL_u/F and CL_r and eGFR, the primary equation for eGFR will be SCr-based:

CKD-Epi equation⁽¹⁾: $eGFR \text{ (mL/min/1.73m}^2\text{)} = 141 \times \min(\text{SCr } / \kappa, 1)^\alpha \times \max(\text{SCr } / \kappa, 1)^{-1.209} \times 0.993^{\text{Age}} \times 1.018 \text{ [if female]} \times 1.159 \text{ [if Black]}$

where:

- SCr is serum creatinine in mg/dL (based on the standardized assay)
- κ is 0.7 for females and 0.9 for males
- α is -0.329 for females and -0.411 for males
- min indicates the minimum of SCr / κ or 1
- max indicates the maximum of SCr / κ or 1
- Age is in years

Additional outputs will also be produced using the following alternative equations to calculate eGFR:

Cockcroft-Gault (CG)⁽²⁾: eGFR (ml/min/1.73 m²) = [(140-Age) \times Weight \times 0.85 if female]/(72 \times SCr)

Modification of Diet in Renal Disease (MDRD)⁽³⁾: eGFR (ml/min/1.73 m²) = 175 \times (SCr)^{-1.154} \times (Age)^{-0.203} \times (0.742 if female) \times (1.212 if black)

where:

- Age is in years
- Weight is in kg
- SCr is in mg/dl (based on the standardized assay)

3.2.2. Safety Endpoints

- *Incidence and severity of treatment-emergent AEs, clinical laboratory abnormalities, vital signs (blood pressure and pulse rate), 12-lead electrocardiogram (ECG) parameters (heart rate, QT, QTcF, PR and QRS intervals).*

An adverse event is considered treatment emergent (TEAE) relative to a given treatment if:

- the event starts during the effective duration of treatment (i.e. starting on or after the dose of PF-06882961 but before this dose plus lag time)

The effective duration of treatment is determined by the lag time. Any event occurring within the lag time is attributed to the corresponding treatment. The lag time is defined by the Pfizer Standard of 365 days post last dose of IP.

A 3-tier approach for summarizing AEs will not be used due to the low number of participants planned to be recruited.

The following data are considered in standard safety summaries (see protocol for collection days and list of parameters):

- adverse events,
- laboratory data,
- vital signs data,
- ECG results.

For laboratory, vital signs and ECG data, baseline will be defined as the last pre-dose measurement on Day 1 or before.

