8. STUDY ASSESSMENTS AND PROCEDURES

Participants will be screened within 28 days prior to administration of the IP to confirm that they meet the study population criteria for the study. The investigator (or an appropriate delegate at the investigator site) must obtain a signed and dated ICD before performing any study-specific procedures.

Study procedures and their timing are summarized in the [SoA](#). Protocol waivers or exemptions are not allowed.

Immediate safety concerns should be discussed with the sponsor immediately upon occurrence or awareness to determine if the participant should continue or discontinue study intervention.

Adherence to the study design requirements, including those specified in the [SoA](#), is essential and required for study conduct.

All screening evaluations must be completed and reviewed to confirm that potential participants meet all eligibility criteria. The investigator will maintain a screening log to record details of all participants screened and to confirm eligibility or record reasons for screening failure, as applicable.

Every effort should be made to ensure that protocol-required tests and procedures are completed as described. However, it is anticipated that from time to time there may be circumstances outside the control of the investigator that may make it unfeasible to perform the test. In these cases, the investigator must take all steps necessary to ensure the safety and well-being of the participant. When a protocol-required test cannot be performed, the investigator will document the reason for the missed test and any corrective and preventive actions that he or she has taken to ensure that required processes are adhered to as soon as possible. The study team must be informed of these incidents in a timely manner.

For samples being collected and shipped, detailed collection, processing, storage, and shipment instructions and contact information will be provided to the investigator site prior to initiation of the study.

The total blood sampling volume for individual participants in this study is approximately 90 mL. The actual collection times of blood sampling may change. Additional blood samples may be taken for safety assessments at times specified by Pfizer, provided the total volume taken during the study does not exceed 550 mL during any period of 60 consecutive days.

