8.3.1. Time Period and Frequency for Collecting AE and SAE Information

The time period for actively eliciting and collecting AEs and SAEs (“active collection period”) for each participant begins from the time the participant provides informed consent, which is obtained before the participant’s participation in the study (ie, before undergoing any study-related procedure and/or receiving study intervention), through and including a minimum of 28 calendar days, except as indicated below, after the last administration of the study intervention.

Follow-up by the investigator continues throughout and after the active collection period and until the AE or SAE or its sequelae resolve or stabilize at a level acceptable to the investigator and Pfizer concurs with that assessment.

For participants who are screen failures, the active collection period ends when screen failure status is determined.

If the participant withdraws from the study and also withdraws consent for the collection of future information, the active collection period ends when consent is withdrawn.

If a participant definitively discontinues or temporarily discontinues study intervention because of an AE or SAE, the AE or SAE must be recorded on the CRF and the SAE reported using the CT SAE Report Form.

Investigators are not obligated to actively seek AE or SAE after the participant has concluded study participation. However, if the investigator learns of any SAE, including a death, at any time after a participant has completed the study, and he/she considers the event to be reasonably related to the study intervention, the investigator must promptly report the SAE to Pfizer using the CT SAE Report Form.

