8.3.1.2. Recording Nonserious AEs and SAEs on the CRF

All nonserious AEs and SAEs occurring in a participant during the active collection period, which begins after obtaining informed consent as described in [Section 8.3.1](#), will be recorded on the AE section of the CRF.

The investigator is to record on the CRF all directly observed and all spontaneously reported AEs and SAEs reported by the participant.

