10.3.1. Definition of AE

AE Definition

• An AE is any untoward medical occurrence in a patient or clinical study participant, temporally associated with the use of study intervention, whether or not considered related to the study intervention.• NOTE: An AE can therefore be any unfavorable and unintended sign (including an abnormal laboratory finding), symptom, or disease (new or exacerbated) temporally associated with the use of study intervention.

Events Meeting the AE Definition

• Any abnormal laboratory test results (hematology, clinical chemistry, or urinalysis) or other safety assessments (eg, ECG, radiological scans, vital sign measurements), including those that worsen from baseline, considered clinically significant in the medical and scientific judgment of the investigator (ie, not related to progression of underlying disease).• Exacerbation of a chronic or intermittent preexisting condition including either an increase in frequency and/or intensity of the condition.• New conditions detected or diagnosed after study intervention administration even though it may have been present before the start of the study.• Signs, symptoms, or the clinical sequelae of a suspected drug-drug interaction.• Signs, symptoms, or the clinical sequelae of a suspected overdose of either study intervention or a concomitant medication. Overdose per se will not be reported as an AE/SAE unless it is an intentional overdose taken with possible suicidal/self-harming intent. Such overdoses should be reported regardless of sequelae.

Events NOT Meeting the AE Definition

• Any clinically significant abnormal laboratory findings or other abnormal safety assessments which are associated with the underlying disease, unless judged by the investigator to be more severe than expected for the participant's condition.• The disease/disorder being studied or expected progression, signs, or symptoms of

the disease/disorder being studied, unless more severe than expected for the participant's condition.

- Medical or surgical procedure (eg, endoscopy, appendectomy): the condition that leads to the procedure is the AE.
- Situations in which an untoward medical occurrence did not occur (social and/or convenience admission to a hospital).

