- If the investigator does not know whether or not the IP caused the event, then the event will be handled as “related to investigational product” for reporting purposes, as defined by the sponsor. In addition, if the investigator determines that an SAE is associated with study procedures, the investigator must record this causal relationship in the source documents and CRF, and report such an assessment in the dedicated section of the CT SAE Report Form and in accordance with the SAE reporting requirements.

Follow-up of AEs and SAEs

- The investigator is obligated to perform or arrange for the conduct of supplemental measurements and/or evaluations as medically indicated or as requested by the sponsor to elucidate the nature and/or causality of the AE or SAE as fully as possible. This may include additional laboratory tests or investigations, histopathological examinations, or consultation with other healthcare professionals.
- If a participant dies during participation in the study or during a recognized follow-up period, the investigator will provide Pfizer Safety with a copy of any postmortem findings including histopathology.
- New or updated information will be recorded in the originally completed CRF.
- The investigator will submit any updated SAE data to the sponsor within 24 hours of receipt of the information.

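### SAP 3.2.2 defines a TEAE by start date alone, so a pre-dose AE that worsens after dosing can be left out of the TEAE summaries

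*SAP*

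**What the plan says.** The secondary safety endpoint in SAP 3.2.2 opens with "Incidence and severity of treatment-emergent AEs". The same section makes an AE treatment-emergent if "the event starts during the effective duration of treatment (i.e. starting on or after the dose of PF-06882961" and before the end of the lag time. On the lag time it says: "The lag time is defined by the Pfizer Standard of 365 days post last dose of IP". This is the only criterion listed. The section defines a pre-dose baseline for laboratory, vital-sign and ECG data, but no baseline severity for AEs. SAP 6.2.2.1 adds no rule on worsening and refers to sponsor reporting standards. The protocol uses the term treatment-emergent without defining it.

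Four parts of the protocol decide what the AE data will look like:

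- Section 8.3.1: active AE collection "begins from the time the participant provides informed consent".
- Section 8.3.1.2: the AE section of the CRF takes "All nonserious AEs and SAEs occurring in a participant during the active collection period".
- Section 8: "Participants will be screened within 28 days prior to administration of the IP".
- Section 10.3.3, on follow-up of AEs: "New or updated information will be recorded in the originally completed CRF".

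Section 10.3.1 counts this among the events that meet the AE definition: "Exacerbation of a chronic or intermittent preexisting condition including either an increase in frequency and/or intensity of the condition".

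**The concern.** AEs are recorded for up to 28 days before dosing, so some may still be open when PF-06882961 is given. If one of them becomes more severe after the dose, that change is what a tolerability summary should show. A test based only on start date does not see it when the event stays on its original record. For laboratory, vital-sign and ECG data the SAP can show a change from the pre-dose state; for AEs it has no equivalent.

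Any such omission lowers the TEAE count and never raises it. It can also remove the highest grade of an event from the severity table. With groups of 6 to 8 participants, one reclassified person is visible in a percentage. Protocol 2.3 says the results will feed into dosing recommendations for renal impairment together with other safety data, so the AE table has a use beyond this report.

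**Working it through.** The plan states no figure on this point, so the check applies the SAP rule to the records that the protocol can generate.

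**Inputs.** The TEAE rule is from SAP 3.2.2. The collection and recording rules are from protocol 8, 8.3.1, 8.3.1.2, 10.3.1 and 10.3.3. Group sizes are from protocol 4.1, Table 1: 8 in each of Groups 1 to 4, and 6 to 8 in Group 5.

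**Applying the rule to four illustrative records.**

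1. Nausea starts 3 hours after the dose. The start is post-dose, so it is counted.
2. A condition in the medical history flares after the dose and is entered as a new AE. The start is post-dose, so it is counted.
3. Mild nausea is recorded as an AE on Day -2, becomes severe 3 hours after the dose, and the original record is updated. The start is pre-dose, so it is not counted.
4. The same course as in 3, but the site enters the worsening as a new AE under the exacerbation item of protocol 10.3.1. The start is post-dose, so it is counted.

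Records 3 and 4 describe the same clinical course and receive different classifications. No text in either document says which recording is required when an AE that is already open worsens.

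**Size for one participant.** Let n be the number in the group. If the excluded event is the participant's only AE after dosing, the change in the group's TEAE incidence is 1/n:

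- n = 8: 1/8 = 0.125, or 12.5 percentage points.
- n = 6 (Group 5 at its minimum): 1/6 = 0.167, or 16.7 percentage points.

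If the participant has another TEAE, the incidence change is 0, and the loss appears only in event counts or the severity table.

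**Frequency.** The documents give neither the proportion of participants with an AE open at dosing nor the proportion of those that worsen. No expected number can be derived from them.

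**The case against.** The strongest reply is that the exclusion is not automatic. The sentence in protocol 10.3.3 about updating the CRF stands among general follow-up duties and does not mention severity changes or onset dates. Protocol 10.3.1 treats an increase in intensity of a preexisting condition as an AE in its own right. It sets aside fluctuations in conditions found at study start only where they do not worsen. A site following that section could open a new record, and the event would count. This part stands: a reader might infer that every worsened pre-dose AE is lost, and the documents do not support that. What remains is that neither recording is required, in a study run at several sites.

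The SAP also leaves some room. SAP 3.2.2 goes on to attribute to treatment any event that occurs within the lag time, which is looser than its start-date test. SAP 6.2.2.1 speaks of adverse events generally and defers to sponsor standards, which are not in the documents and may contain a worsening rule. Neither removes the gap in the written definition.

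A reader might also infer that the loss would concentrate in Groups 4 and 5, because those participants are sicker. The documents do not show this. Complaints that predate consent are medical history, and a flare entered as a new AE is counted. The exposed case is narrower: an AE that began between consent and dosing, was still open at dosing, then worsened and stayed on the old record.

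A probability of at least one such case can be produced only by assuming rates. For example, if 5% to 15% have an AE open at dosing and 10% to 30% of those worsen, the chance runs from 1 - (1 - 0.005)^38 = 17% to 1 - (1 - 0.045)^40 = 84%. That range restates the assumptions and is not evidence.

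Finally, the 365-day lag far exceeds the 28-35 day follow-up contact, and a reader might want it shortened. No bias follows from the long window. Shortening it would remove late SAEs judged related to the drug, which protocol 8.3.1 requires to be reported, from the TEAE count.

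**Conclusion.** The point holds in a limited form. The written TEAE definition can misclassify an AE that was open at dosing and worsened afterwards, and the outcome depends on how the site records it. The effect is 12.5 points (n = 8) or 16.7 points (n = 6) of a group's TEAE incidence for each participant who has no other TEAE. For anyone else, only event counts or the severity table are affected. This rests on two conditions: the worsening stays on the original record, and no unseen sponsor standard already covers it. How often the case will arise is unknown.

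The endpoint is secondary and descriptive. SAP 5.1 plans no hypothesis testing and SAP 6.2.2 plans no formal safety analysis. The PK endpoints and the sample size are untouched. This is a minor improvement that is worth making because it is nearly free.

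**What to change.** In SAP 3.2.2, define a TEAE as an AE that starts on or after the dose of PF-06882961, or that started before the dose and increased in severity on or after it. Summarise events of the second kind at their worst post-dose severity. Keep the existing lag time.

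An optional alternative, not needed in addition, is a CRF completion instruction that a post-dose increase in severity of an open AE be entered as a new record with its own start date and time; the present SAP rule would then count it. This is the more practical route if the AE record would not show when the severity changed.

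The cost is one SAP clause, with no new procedures. The TEAE count may rise slightly, and the rule departs from the start-date-only definition.
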